#### 4. Tim to alleviation of baseline symptoms

First day of participant level alleviation status equals Yes. If a participant has not achieved symptom alleviation at last FLuPRO assessment, the participant will be censored at the date of last FLUpro assessment. For symptom alleviation of a domain, the last assessment date is only among those baseline symptoms within the domain.

#### 19) Covid-19 medications include:

Chloroquine, Hydroxychloroquine, IV remdesivir, Bamlanivimab, Casirivimab/Imdevimab, Molnupiravir, Lopinavir-ritonavir, Ribavirin. Details of COVID-19 medications are provided in table below.

Drug name	ATC Code	WHODRUG Preferred Term
Chloroquine	P01BA	CHLOROQUINE
Hydroxychloroquine	P01BA	HYDROXYCHLOROQUINE
Lopinavir/ritonavir	J05AR	LOPINAVIR/RITONAVIR
Ribavirin	J05AP	RIBAVIRIN
Remdesivir	J05AB	REMDESIVIR
Bamlanivimab	--	BAMLANIVIMAB
Casirivimab/Imdevimab	--	CASIRIVIMAB/IMDEVIMAB
Molnupiravir	--	MOLNUPIRAVIR

ATC = anatomical therapeutic chemical

Additional medication may be included during final review of Concomitant medications prior to data finalization.

#### 20) Baseline risk factor

Selected medical history will be summarized as baseline risk factor and be included as subgroups in analysis. A risk factor for a participant is defined as a medical history of one of these diseases:

- At least 1 ongoing medical history record with MedDRA PT (mh.MDRPT) in the following selected PT listing for the corresponding disease with start date on or prior to the first dose date.
- At least 1 ongoing AE record with MedDRA PT (ae.MDRPT) in the following selected PT listing for the corresponding disease with start date on or prior to the first dose date

If the start date is incomplete but the month and year (or year alone) of the start date is the same as or before the month and year (or year alone) of the first dosing date of study drug, the event will be included. If the start date is completely missing, the event will be included.

A variable for each of the risk factors will be added to raw Medical History and Adverse Events datasets. A medical history or an AE record will be flagged for a risk factor if its MedDRA PT included in the prespecified PT list for the corresponding disease of interest, which include all PTs from the narrow or broad search of the following SMQs under MedDRA 24.0 provided by Gilead GLPS and reviewed by Gilead medical monitors.

Disease of Interest	SMQ or MedDRA HLT Source
Chronic lung disease	HLT of bronchospasm and obstruction
Hypertension	Hypertension (SMQ)
Cardiovascular or cerebrovascular disease	Ischaemic central nervous system vascular conditions (SMQ); Myocardial infarction (SMQ); Other ischaemic heart disease (SMQ)
Diabetes mellitus	Hyperglycaemia/new onset diabetes Mellitus (SMQ)
Immunocompromised state	HLGT for “Immunodeficiency syndromes”
Chronic mild or moderate kidney disease	Chronic kidney disease (SMQ)
Chronic liver disease	search name “Chronic liver disease excluding transient_acute events and nonspecific signs_symptoms
Current cancer	Malignancies (SMQ)
Sickle cell disease	HLGT “Haemoglobinopathies”

Risk factor of obesity will be defined as BMI  $\geq 30$  kg/m^2 at baseline based on CRF data.

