### 4.2. Inclusion Criteria

Participants must meet all of the following inclusion criteria to be eligible for participation in this study:

- 1) Willing and able to provide written informed consent (participants  $\geq$  18 years of age) or assent (participants  $\geq$  12 and  $<$  18 years of age) prior to performing study procedures. Participants aged  $\geq$  18 years may be enrolled with the consent of a legal representative where permitted according to local law and approved nationally and by the relevant institutional review board (IRB) or independent ethics committee (IEC). For participants  $\geq$  12 and  $<$  18 years of age, a parent or legal guardian must be willing and able to provide written informed consent prior to performing study procedures
- 2) Either:
  - Age  $\geq$  18 years (at all sites) or aged  $\geq$  12 and  $<$  18 years of age weighing  $\geq$  40 kg (where permitted according to local law and approved nationally and by the relevant IRB or IEC) with at least 1 of the following pre-existing risk factors for progression to hospitalization:
    - a) Chronic lung disease: chronic obstructive pulmonary disease, moderate-to-severe asthma, cystic fibrosis, pulmonary fibrosis
    - b) Hypertension: systemic or pulmonary
    - c) Cardiovascular or cerebrovascular disease: coronary artery disease, congenital heart disease, heart failure, cardiomyopathy, history of stroke, atrial fibrillation, hyperlipidemia
    - d) Diabetes mellitus: Type 1, type 2, or gestational
    - e) Obesity (BMI  $\geq$  30)
    - f) Immunocompromised state; having a solid organ transplant, blood, or bone marrow transplant; immune deficiencies; HIV with a low CD4 cell count or not on HIV treatment; prolonged use of corticosteroids; or use of other immune weakening medicines
    - g) Chronic mild or moderate kidney disease
    - h) Chronic liver disease

- i) Current cancer
- j) Sickle cell disease

OR age  $\geq$  60 years, regardless of the presence of other pre-existing risk factors for progression

- 3) SARS-CoV-2 infection confirmed by molecular diagnostics (nucleic acid [eg, PCR] or antigen testing)  $\leq$  4 days prior to screening
- 4) Presence of  $\geq$  1 symptom(s) consistent with COVID-19 for  $\leq$  7 days prior to randomization (such as fever, cough, fatigue, shortness of breath, sore throat, headache, myalgia/arthralgia) {[Stokes 2020](#), [World Health Organization \(WHO\) 2020b](#)}

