### **3.4. Examination of Subject Subgroups**

The primary endpoint will be examined for the following participant subgroups:

- region (US vs. ex-US)
- participant's age (<18, 18≤ - < 60, ≥ 60 years),
- participants who reside in a skilled nursing facility (Yes, No),
- Sex at birth: (a) male and (b) female
- Race: (a) Asian, (b) Black, (c)White, (d) other
- Baseline risk factor: Chronic lung disease (Yes, No), Hypertension (Yes, No), Cardiovascular or cerebrovascular disease (Yes, No), Diabetes mellitus (Yes, No), Obesity (Yes, No), Immunocompromised state (Yes, No), Chronic mild or moderate kidney disease (Yes, No), Chronic liver disease (Yes, No), Current cancer (Yes, No), Sickle cell disease (Yes, No)
- Common COVID-19 symptoms at baseline: absence or presence for each of the following symptoms: Stuffy or runny nose; Sore throat; Shortness of breath (difficulty breathing); Cough; Low energy or tiredness; Muscle or body aches; Headache; Chills or shivering; Feeling hot or feverish; Nausea; Vomit; Diarrhea; Loss of Smell; Loss of taste.

In addition, other subgroups may be considered based on imbalances between treatment groups observed in other baseline characteristics.

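### The SAP derives baseline risk factors from ongoing records only, so a past stroke, which qualifies a participant for entry, can be coded as no cardiovascular or cerebrovascular disease

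*SAP*

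**What the plan says.** Protocol 4.2, criterion 2c, lists the cardiovascular and cerebrovascular conditions that qualify a participant: coronary artery disease, then "congenital heart disease, heart failure, cardiomyopathy, history of stroke, atrial fibrillation, hyperlipidemia". SAP 1.2 repeats the list.

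SAP Appendix 2, item 20, turns these conditions into analysis flags. It contains three statements about what counts:

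- The lead-in: "A risk factor for a participant is defined as a medical history of one of these diseases".
- Two participant-level routes, each also requiring a start date on or before the first dose: "At least 1 ongoing medical history record with MedDRA PT (mh.MDRPT" and "At least 1 ongoing AE record with MedDRA PT (ae.MDRPT".
- A record-level sentence: "A medical history or an AE record will be flagged for a risk factor if its MedDRA PT included in the prespecified PT list".

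For cardiovascular or cerebrovascular disease the search groups are "Ischaemic central nervous system vascular conditions (SMQ); Myocardial infarction (SMQ); Other ischaemic heart disease (SMQ".

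The flag is used in two places. SAP 3.4 lists "Cardiovascular or cerebrovascular disease (Yes, No" among the subgroups for the primary endpoint. SAP 5.2 summarizes the risk factors by treatment group, with a CMH comparison.

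**The concern.** A history of stroke is a past event by its own wording, and participants in this trial are outpatients who do not currently need hospital care. Item 20 searches for ischaemic cerebrovascular terms and then keeps only records marked ongoing. A stroke that qualified the participant for entry can be found by the search and then dropped by the status filter. A complete term list would not prevent this, because the loss comes from the status requirement.

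At stake are a baseline table that under-reports one of the qualifying risk factors, and a subgroup whose 'No' level holds some participants with the disease. Item 20 also leaves room for two programmers to derive different variables, because its lead-in and record-level sentence do not carry the ongoing condition.

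**Working it through.** The plan states no figure on this point, so the main check is a comparison of texts.

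**Step 1. Can a resolved stroke reach 'Yes'?**

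| Statement | Needs an ongoing record? | Resolved stroke counted? |
|---|---|---|
| Criterion 2c (Protocol 4.2) | No | Yes |
| Item 20, lead-in | No | Yes |
| Item 20, medical history route | Yes | No |
| Item 20, AE route | Yes | No |
| Item 20, record-level sentence | No, term match only | Record flagged |

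The AE route does not rescue the case. It also requires an ongoing record, and SAP 5.3 places conditions with onset before consent in medical history.

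**Step 2. Does the narrowing look intended?** Where the criterion wants current disease only, it says so, as it does for cancer. Where item 20 wants acute events left out, it also says so, as in its chronic liver disease search. The cardiovascular row has no such limit, and one of its groups is named for an event, myocardial infarction. A single status filter appears to have been applied to every disease.

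**Step 3. Conditions for miscoding.** Both must hold: the past event is entered as not ongoing, and the participant has no other ongoing record on the list. A participant with a past infarction and ongoing coronary disease can still be 'Yes' through the other ischaemic heart disease group.

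**Step 4. Illustration of size.** The only input from the documents is N = 584 randomized (SAP 2.1.1). The analysis sets require a dose, so they can only be the same size or smaller. Two inputs are assumed: p, the share of participants with the disease on the listed terms; and s, the share of those whose listed records are all not ongoing.

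- Moved from 'Yes' to 'No': M = N × p × s
- Share of the coded 'No' level: M / (N − N × p + M)

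| p | True 'Yes' | M at s = 10% | M at s = 50% | Share of 'No' |
|---|---|---|---|---|
| 5% | 29 | 3 | 15 | 0.5% to 2.6% |
| 10% | 58 | 6 | 29 | 1.1% to 5.3% |
| 20% | 117 | 12 | 58 | 2.4% to 11.1% |

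For the last entry: 584 × 0.20 × 0.50 = 58.4, and 58.4 / (584 − 116.8 + 58.4) = 0.111.

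**Step 5. Effect on the subgroup estimates.** 'Yes' loses a fraction s of its members. If they have the same event rate as those kept, the standard error of the log hazard ratio in 'Yes' grows by a factor of 1/√(1 − s): 1/√0.9 = 1.05 at s = 10%, and 1/√0.5 = 1.41 at s = 50%. In 'No', the log hazard ratio is roughly (1 − w) times that of true non-cases plus w times that of the moved participants, where w is the moved participants' share of the events in 'No'. It shifts only if the two hazard ratios differ.

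**The case against.** The strongest reply is that miscoding is conditional. Neither document defines ongoing or shows how a past stroke is entered on the eCRF. If sites leave such records open, nothing is lost. Item 20 also says that medical monitors reviewed the term lists, and its lead-in and record-level sentence could be read as governing. This stands as a limit: the loss is possible under the stated rule and is not shown to occur. It does not remove the conflict, because the participant-level bullets are explicit and the result should not depend on how a site fills in a status field.

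The reach is also small. The flag feeds one row of a baseline table and one of many unadjusted subgroups, which SAP 6.1.3 says may be analyzed. That stands in full.

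A reader might infer more than the documents support:

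- **That criterion 2c means past infarction as it means past stroke.** It names coronary artery disease, not infarction. The infarction case rests on the SAP's choice of search group.
- **That both subgroup hazard ratios are pulled together.** Movement is one way, from 'Yes' to 'No'. No participant without the disease enters 'Yes', and nothing shows that those lost respond differently from those kept.
- **That 'Yes' loses a quarter to nearly half of its members.** Suppose 2% to 5% of 584 (12 to 29) have only a resolved event and 6% (35) hold an ongoing term. The loss is then 2/8 = 25% to 5/11 = 45%. Each of these inputs is assumed, and the same inputs put only 12/549 = 2.2% to 29/549 = 5.3% of 'No' in the wrong level.
- **That affected participants would look ineligible.** The flags are factor by factor and do not determine eligibility. Age 60 or over qualifies on its own.

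**Conclusion.** The point holds as a conditional misclassification. Under the participant-level rule of item 20, a participant whose only listed record is a past stroke entered as not ongoing is coded 'No', contrary to criterion 2c and to the item's own lead-in. The same can happen to a past infarction with no ongoing coronary term.

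The consequence is an under-counted 'Yes' level with wider confidence intervals, and a 'No' level that includes some participants with the disease. The documents give neither the prevalence nor the share of resolved records, so the range of 3 to 58 participants only illustrates p from 5% to 20% and s from 10% to 50%.

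The rule is identical in both arms. The primary Cox model uses only the stratification factors, so a reader should not infer bias in the primary result. Strata, eligibility and sample size are also unaffected. This is a minor correction worth making because it is cheap.

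**What to change.** In item 20, add a rule specific to the cardiovascular or cerebrovascular flag: any listed medical history record counts, ongoing or past, if it starts on or before the first dose. Keep the ongoing condition for cancer, where the criterion says current. State which sentence defines the participant-level variable, and make the lead-in, the two routes and the record-level sentence agree. Do this before unblinding and enter it in the SAP revision table.

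The cost is a short disease-specific paragraph and one program filter. No new data are needed, because Protocol 6.2.1 already collects full medical history at screening. The downside is that remote, fully resolved events will also count, which criterion 2c already accepts for stroke.

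The change does not by itself align the flag with criterion 2c. By their titles the three search groups are all ischaemic, while the criterion also lists conditions such as heart failure and atrial fibrillation. That is a separate question about the term list.

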#### **5.3.2. Infusion-related Reactions**

Infusion-related reactions have been observed during and following administration of RDV. Signs and symptoms may include hypotension, hypertension, tachycardia, bradycardia, hypoxia, fever, dyspnea, wheezing, angioedema, rash, nausea, diaphoresis, and shivering. Slower infusion rates, with a maximum infusion time of up to 120 minutes, can be considered to potentially prevent these signs and symptoms. If signs and symptoms of a severe infusion-related reaction occur, immediately discontinue administration of RDV and initiate appropriate treatment. Please refer to Section [7.6](#).

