### **7.3. Investigator Requirements and Instructions for Reporting Adverse Events and Serious Adverse Events**

#### **7.3.1. Requirements for Collection Prior to Study Drug Initiation**

After informed consent, but prior to initiation of study medication, the following types of events must be reported on the applicable eCRFs: all SAEs and AEs related to protocol-mandated procedures.

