### **8.6.2. Adverse Events**

Clinical and laboratory AEs will be coded using the Medical Dictionary for Regulatory Activities. System Organ Class, High-Level Group Term, High-Level Term, Preferred Term, and Lower-Level Term will be attached to the clinical database.

Events will be summarized on the basis of the date of onset for the event. A treatment-emergent AE will be defined as any AE that begins on or after the randomization date up to the date of last dose of study drug plus 30 days.

Summaries (number and percentage of participants) of treatment-emergent AEs (by system organ class and preferred term) will be provided by treatment group.

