#### **7.1.6.1.      Definition of Treatment-Emergent Adverse Events**

Treatment-emergent adverse events (TEAEs) are defined as 1 or both of the following:

- Any AEs with an onset date on or after the study drug start date and no later than 30 days after permanent discontinuation of study drug
- Any AEs leading to premature discontinuation of study drug.

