#### **7.1.6.2.      Incomplete Dates**

If the onset date of the AE is incomplete and the AE stop date is not prior to the first dosing date of study drug, then the month and year (or year alone if month is not recorded) of onset determine whether an AE is treatment emergent. The event is considered treatment emergent if both of the following 2 criteria are met:

- The AE onset date is the same as or after the month and year (or year) of the first dosing date of study drug, and
- The AE onset date is the same as or before the month and year (or year) of the date corresponding to 30 days after the date of the last dose of study drug

An AE with completely missing onset and stop dates, or with the onset date missing and a stop date later than the first dosing date of study drug, or with the onset date missing and the AE is marked as ongoing, will be considered to be treatment emergent. In addition, an AE with the onset date missing and incomplete stop date with the same or later month and year (or year alone if month is not recorded) as the first dosing date of study drug will be considered treatment emergent.

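### An ongoing adverse event dated to Day 1, or with a missing or same-period partial start date, can count as both a treatment-emergent AE and a baseline risk factor

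*SAP*

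**What the plan says.** SAP Appendix 2, item 20 gives two routes to a risk-factor flag. One is an ongoing medical history record. The other is "At least 1 ongoing AE record with MedDRA PT (ae.MDRPT) in the following selected PT listing", where the record is "for the corresponding disease with start date on or prior to the first dose date". Incomplete start dates are accepted if the known month and year, or the year alone, is no later than that of first dose. For dates with no information the rule is "If the start date is completely missing, the event will be included". Obesity is the exception and comes from baseline BMI. The other nine factors use term lists.

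SAP 7.1.6.1 defines as treatment-emergent "Any AEs with an onset date on or after the study drug start date", up to 30 days after study drug is stopped for good. SAP 7.1.6.2 extends this to partial onset dates that match the month or year of first dose, and to an AE "with the onset date missing and the AE is marked as ongoing, will be considered to be treatment emergent". The protocol's own definition (8.6.2) starts earlier still: "any AE that begins on or after the randomization date up to the date of last dose of study drug plus 30 days".

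Before first dose, protocol 7.3.1 limits AE reporting to "all SAEs and AEs related to protocol-mandated procedures". Protocol 5.3.2 says of infusion-related reactions: "Signs and symptoms may include hypotension, hypertension, tachycardia, bradycardia, hypoxia, fever, dyspnea, wheezing", among others.

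The flags are used in SAP 5.2 (baseline summaries compared between arms) and SAP 3.4 (subgroups of the primary endpoint). SAP 3.3 adds that imbalances in baseline characteristics may be taken up as covariates in sensitivity analyses.

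**The concern.** A baseline variable should be fixed before treatment can act on it. Item 20 and the treatment-emergent rule both include the first dose date, both work on calendar dates without clock time, and both take in missing and same-period partial dates. Nothing removes a treatment-emergent record from item 20. One record can therefore appear in the safety tables as an event on treatment and in the baseline table as a pre-existing condition.

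If such a record reflects a post-dose event, the subgroup it defines is partly formed after randomization and the comparison within it is no longer fully protected. A drug effect could also show up as a baseline difference between arms and then be adjusted for in a sensitivity analysis.

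**Working it through.** There is no stated figure to reproduce. The check runs the two definitions on the same records.

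**Rules for an ongoing AE with a listed preferred term**
- Item 20: flag if start date ≤ first dose date. A partial date is flagged if its month and year (or year) ≤ that of first dose. A missing date is flagged.
- SAP 7.1.6, onset rule: treatment-emergent if first dose date ≤ onset ≤ last dose date + 30 days. A partial date is compared by month and year (or year). A missing date on an ongoing AE is treatment-emergent.

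**Illustrative dates:** first dose 10 February 2021, last dose 12 February, window end 12 February + 30 days = 14 March 2021.

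| Recorded start date | Baseline risk factor | Treatment-emergent | Both |
|---|---|---|---|
| 7, 8 or 9 February | yes | no | no |
| 10 February (Day 1) | yes | yes | **yes** |
| 11 to 15 February | no | yes | no |
| January 2021, day missing | yes | no | no |
| February 2021, day missing | yes | yes | **yes** |
| 2021, day and month missing | yes | yes | **yes** |
| Completely missing | yes | yes | **yes** |

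With complete dates the overlap is exactly one calendar day, Study Day 1. With incomplete dates it is wider: an event that began on 20 February, ten days after first dose, but was recorded only as February 2021 would be flagged as baseline.

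SAP 7.1.6.1 has a second limb, AEs leading to premature discontinuation of study drug, which carries no onset limit. A pre-dose AE of that kind would also be in both classes, but it is a genuine baseline condition and not part of the problem. Under the protocol's start at randomization, which 5.1.1 allows about one day before Day 1, the overlap would reach back to that date; those extra records would be pre-dose.

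**Comparison with the SAP's own convention.** SAP 3.8.1 takes baseline as the last value at or before first dose, using clock time where recorded, and Table 3-1 splits Day 1 into pre-dose and post-dose. Item 20 does neither.

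**What each repair does.** Changing item 20 to a start date strictly before first dose removes the Day 1 row only; the partial- and missing-date rows stay in both classes. Excluding treatment-emergent records removes all four overlapping rows and keeps the January 2021 record.

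**Scale.** SAP 2.1.1 reports 584 randomized, so about 584 / 2 = 292 per arm. Each misclassified participant moves that arm's percentage for a risk factor by 1 / 292 = 0.34 percentage points. As an illustration only, 0 to 5 such participants in one arm would move it by 0 to 5 / 292 = 1.7 points.

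**The case against.** The case on the other side has several sound parts.

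- **A Day 1 date does not prove post-dose onset.** Protocol 6.3 puts AE review among the assessments due before dosing on Day 1. Protocol 7.1.1 treats a pre-existing condition that worsens after consent as an AE, although 6.2.1 sends screening-period exacerbations to medical history. A reader might infer from the narrow pre-dose AE collection that nearly every AE caught by item 20 is post-dose. The documents do not support that.
- **The ongoing condition limits the reach.** A transient infusion reaction that resolves leaves no ongoing record, and protocol 7.3.2 asks for follow-up to resolution or stability where possible. This stands, although item 20 does not say as of when the record must be ongoing.
- **Many affected participants would be flagged anyway.** Hypertension, diabetes and chronic lung disease are entry criteria, so a matching medical history will often exist.
- **The link to drug reactions is narrow.** One might add wheezing and hyperglycaemia to the example. Whether wheezing falls under item 20's bronchospasm term depends on the MedDRA hierarchy, which the documents do not give, and protocol 5.3.2 does not name hyperglycaemia. Only hypertension is shown by the text on both sides.
- **No imbalance between arms is shown.** Placebo has the same inactive ingredients (protocol 5.2.1), is infused on the same days, and is given to people with the same acute illness, so such records can arise in both arms. No rate by arm can be derived.
- **Missing dates should be few,** given the verification and queries in protocol 9.1.7.

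These points reduce the likely size. They do not remove the overlap in the definitions.

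**Conclusion.** The overlap is real and follows from the text alone: Day 1, same-month or same-year partial dates, and missing dates put one ongoing, listed AE in both classes. It is a minor point. It touches only the baseline risk-factor summaries, the risk-factor subgroups of the primary endpoint (which SAP 6.1.3 says may be analyzed) and any optional covariate sensitivity analysis.

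A reader might infer that the primary result is at risk. It is not: the Cox model in SAP 6.1.3 and Appendix 2, item 25 adjusts only for the three stratification factors. The number of affected records cannot be obtained from the documents and may be near zero, and the direction of any imbalance is unknown. The effect would be most visible in a small subgroup, where a few participants can be a large share.

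**What to change.** In item 20, add that an AE record which is treatment-emergent under SAP 7.1.6, including through the missing- or partial-date rules, does not set a risk factor. Keep an AE record only if its onset is before the first dose date (and time, if available), in line with SAP 3.8.1. Otherwise derive the flags from medical history and baseline BMI. State as of when a record must be ongoing.

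Because 7.1.6.1 works on dates, the exclusion removes every Day 1 AE whatever its clock time; time would matter only if that definition also became time-based.

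The cost is a sentence in the SAP and one program condition. What is lost is the rare pre-dose condition recorded only as an AE with a Day 1 or incomplete date, and, through the discontinuation limb of 7.1.6.1, a pre-dose AE that later led to stopping study drug. A chronic disease that worsened after consent should not be lost, since SAP 5.3 places conditions with onset before consent in medical history.

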## 1.2. Study Design

This is a Phase 3, randomized, double-blind, placebo-controlled, multicenter study of RDV therapy for outpatients with early stage COVID-19 who are at higher risk of disease progression.

Participants who meet all eligibility criteria may be randomized in a 1:1 ratio to RDV or placebo. Randomization will be stratified by participants who reside in a skilled nursing facility, by participant's age (< 60 vs  $\geq$ 60 years), and by region (United States [US] vs. ex-US):

**Treatment Group A:** single dose of IV RDV 200 mg on Day 1 followed by IV RDV 100 mg on Days 2 and 3 (RDV group)

**Treatment Group B:** IV placebo-to-match (PTM) RDV on Days 1 to 3 (PTM group)

Participants must meet all of the following inclusion criteria to be eligible for participation in this study:

- 1) Willing and able to provide written informed consent (participants  $\geq$  18 years of age) or assent (participants  $\geq$  12 and < 18 years of age) prior to performing study procedures. Participants aged  $\geq$  18 years may be enrolled with the consent of a legal representative where permitted according to local law and approved nationally and by the relevant institutional review board (IRB) or independent ethics committee (IEC). For participants  $\geq$  12 and < 18 years of age, a parent or legal guardian must be willing and able to provide written informed consent prior to performing study procedures
- 2) Either:
  - Age  $\geq$  18 years (at all sites) or aged  $\geq$  12 and < 18 years of age weighing  $\geq$  40 kg (where permitted according to local law and approved nationally and by the relevant IRB or IEC) with at least 1 of the following pre-existing risk factors for progression to hospitalization:
    - a) Chronic lung disease: chronic obstructive pulmonary disease, moderate-to-severe asthma, cystic fibrosis, pulmonary fibrosis
    - b) Hypertension: systemic or pulmonary
    - c) Cardiovascular or cerebrovascular disease: coronary artery disease, congenital heart disease, heart failure, cardiomyopathy, history of stroke, atrial fibrillation, hyperlipidemia
    - d) Diabetes mellitus: Type 1, type 2, or gestational
    - e) Obesity (BMI  $\geq$  30)

- f) Immunocompromised state; having a solid organ transplant, blood, or bone marrow transplant; immune deficiencies; HIV with a low CD4 cell count or not on HIV treatment; prolonged use of corticosteroids; or use of other immune weakening medicines
- g) Chronic mild or moderate kidney disease

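### Several baseline risk-factor flags come from MedDRA groups that, by name, do not match the entry criteria whose labels they carry; cardiovascular disease is the clearest case

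*SAP*

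**What the plan says.** Criterion 2 in Protocol 4.2 defines most of its risk factors by named conditions. Cardiovascular or cerebrovascular disease (2c) is "coronary artery disease, congenital heart disease, heart failure, cardiomyopathy, history of stroke, atrial fibrillation, hyperlipidemia", and SAP 1.2 repeats this list. Chronic lung disease (2a) is "chronic obstructive pulmonary disease, moderate-to-severe asthma, cystic fibrosis, pulmonary fibrosis". The immunocompromised criterion (2f) includes transplant, prolonged steroid use and other medicines that weaken immunity.

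SAP 3.4 uses the same labels as Yes/No subgroups and says the primary endpoint will be examined in them. SAP 5.2 puts the same factors in the baseline table.

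SAP Appendix 2 item 20 then gives the derivation. A participant has a factor if there is "At least 1 ongoing medical history record with MedDRA PT (mh.MDRPT) in the following selected PT listing" for that disease, or an equivalent adverse-event record, starting on or before the first dose date. A record is flagged when its term is "included in the prespecified PT list for the corresponding disease of interest". The terms are described as those "which include all PTs from the narrow or broad search of the following SMQs under MedDRA 24.0". For cardiovascular or cerebrovascular disease the sources are "Ischaemic central nervous system vascular conditions (SMQ); Myocardial infarction (SMQ); Other ischaemic heart disease (SMQ"; for chronic lung disease, "HLT of bronchospasm and obstruction". The immunocompromised flag comes from a group for immunodeficiency syndromes, the sickle cell flag from a group for haemoglobinopathies, and the diabetes flag from a group that also names hyperglycaemia. Obesity is defined directly by BMI.

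**The concern.** A reader of the risk-factor table or a subgroup row will take a label worded like an entry criterion to mean that criterion. Under the groups as named, it may not.

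Participants under 60 can enter only through 2a to 2j. One who entered solely because of atrial fibrillation or pulmonary fibrosis could be 'No' on every flag, so the table could appear to show people enrolled without a qualifying condition. In the other direction, a participant with a haemoglobinopathy other than sickle cell disease could be counted as having sickle cell disease.

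What is at stake is the accuracy of the baseline description and of the risk-factor subgroup rows. SAP 5.3 also tabulates every medical-history preferred term, but it does not group terms by risk factor or feed the subgroups.

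**Working it through.** No figure in the plan bears on this point, so the check is a comparison of names, followed by a rough sizing.

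**Criteria against sources**

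| Flag | Source as named in item 20 | In the criterion but not named by the source | Named by the source beyond the criterion |
|---|---|---|---|
| Cardiovascular or cerebrovascular | Three groups, ischaemic or infarction | Heart failure, atrial fibrillation, cardiomyopathy, congenital heart disease, hyperlipidemia (5 of 7) | None |
| Chronic lung disease | Bronchospasm and obstruction | Pulmonary fibrosis, cystic fibrosis (2 of 4) | No severity limit on asthma |
| Immunocompromised state | Immunodeficiency syndromes | Transplant, prolonged corticosteroids, other immune-weakening medicines; no medication data are used | None |
| Sickle cell disease | Haemoglobinopathies | None | The wider class |
| Diabetes mellitus | Hyperglycaemia and new-onset diabetes | None clear from the name | Hyperglycaemia |

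Criterion 2c also accepts a past stroke, while item 20 requires an ongoing record. Whether past strokes are lost depends on how sites record them, which the documents do not show.

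SAP 3.4 lists ten risk factors. Obesity uses BMI, so 10 − 1 = 9 are derived from MedDRA groups. The table covers the five that differ by name.

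**How small the subgroup rows are**

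Inputs: 584 randomized (SAP 2.1.1); planned pooled event rate 9.3% and placebo rate 12% (Protocol 8.9, SAP 1.3). SAP 2.3 says hospitalization rates had fallen but gives no figure, so half the planned pooled rate, 4.65%, is added as an assumption.

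Expected events = number randomized × event rate:

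- Planned pooled rate: 584 × 0.093 = 54.3
- 12% in both arms (no treatment effect): 584 × 0.12 = 70.1
- Half the planned pooled rate: 584 × 0.0465 = 27.2

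Events in a 'Yes' group = 584 × prevalence × event rate. Prevalences of 5% and 20%, and an average event rate among those with the factor, are assumptions:

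| Prevalence | 'Yes' participants | Events at 4.65% | Events at 9.3% | Events at 12% |
|---|---|---|---|---|
| 5% | 29.2 | 1.4 | 2.7 | 3.5 |
| 20% | 116.8 | 5.4 | 10.9 | 14.0 |

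The Full Analysis Set also requires a dose, so at these same rates its figures can only be equal or lower.

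**Reach**

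The primary Cox model in SAP 6.1.3 and Appendix 2 item 25 contains treatment and the three stratification factors only. None of these flags enters it.

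**The case against.** The strongest objection is that the term lists are not in the documents. Item 20 calls the listing selected and prespecified, and says medical monitors reviewed it. Terms may have been added beyond the named groups, or selected within them; the haemoglobinopathy list may already be cut to sickle cell terms. The statement that all terms are included speaks of SMQs, whereas the lung source is an HLT and the immunocompromised and sickle cell sources are HLGTs. This stands: it limits the point to a mismatch by name and leaves the cardiovascular flag, whose sources are all SMQs, as the firmest case. It does not remove the point, because item 20 states no addition or restriction that would close the gap.

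It can also be said that nothing in SAP 3.4 or 5.2 promises to reproduce the entry criteria, and that item 20 discloses its sources. A narrower cardiovascular flag may even be preferred, since adding hyperlipidemia could dilute it. That is a legitimate choice, but the label should then say so.

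Three stronger readings are tempting and not supported:

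- **The hypertension and kidney flags fail too.** An unqualified hypertension group does not by name exclude pulmonary hypertension. Exclusion criterion 7 keeps out creatinine clearance or eGFR below 30, so the absence of a mild-or-moderate limit in the kidney source has little effect.
- **The subgroup analyses are only optional.** The 'may' in SAP 6.1.3 refers to subgroups in Section 3.3; Section 3.4, where they are listed, says the endpoint will be examined in them.
- **About 54 events is a ceiling.** The 9.3% rate already assumes the planned benefit; 12% in both arms gives about 70.

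**Conclusion.** The point holds by name, and clearly for the cardiovascular or cerebrovascular flag. The lung, immunocompromised and sickle cell flags show the same kind of mismatch, subject to term lists that are not shown. Diabetes and past stroke are lesser points of the same kind.

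The number of participants misclassified cannot be computed, and a reader should not infer that misclassification has been shown to occur. What can be said is that the rows are small: roughly 27 to 70 events in the whole trial across the three rates considered, and about 1 to 14 in a 'Yes' group at the assumed prevalences. A few misplaced participants could therefore alter a row.

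Eligibility, the Full Analysis Set, the primary Cox test, alpha and power are unchanged. This is a matter of accurate labelling and description, worth correcting because correction is cheap.

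**What to change.** Before unblinding, compare the cardiovascular, lung, immunocompromised, sickle cell and diabetes term lists with criterion 2. Then, for each flag, do one of the following.

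- **Align it.** Add the listed conditions that are omitted, restrict the sickle cell flag to sickle cell terms, and accept past as well as ongoing stroke records.
- **Relabel it.** Where the data cannot support the criterion, or the narrower definition is intended, name the flag for what is searched, such as 'ischaemic cardiovascular or cerebrovascular disease' or 'immunodeficiency syndrome', and footnote the difference. This suits asthma severity and the medication routes in 2f: Protocol 5.4 records medicines from 30 days before screening, which may not establish prolonged use.

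If the reviewed lists already go beyond, or narrow, the named groups, say so in item 20 and append them.

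The cost is one further term-list review and minor programming or label edits. No new data collection is needed, since full medical history is already taken at screening (Protocol 6.2.1).
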